4.3. Outcome Definitions

4.3.1. Pregnancy Outcomes of Interest

The following pregnancy outcomes will be collected by the registry:

- Spontaneous miscarriage: fetal death or expulsion of products of conception prior to 20 weeks' (<20 weeks) gestation
- Live birth: the birth of a living fetus at 20 weeks' gestation or greater (\geq 20 weeks), or, if gestational age is unknown, a fetus weighing 500 g or more (\geq 500 g)
- Stillbirth: a fetal death occurring at 20 weeks' gestation or greater (≥20 weeks), or, if gestational age is unknown, a fetus weighing 500 g or more (≥500 g)
- Elective termination: voluntary interruption of pregnancy, including pregnancy termination that occurs electively, to preserve maternal health, or due to fetal abnormalities
- Preterm birth: an infant born at gestational age less than 37 weeks (<37 weeks)
- Neonatal death: an infant who after live birth expired within the first 28 days (≤28 days) of life
- Ectopic pregnancy: implantation of a conception outside of the uterus
- Molar pregnancy: a conception that results in a gestational trophoblastic tumor
- Small for gestational age (SGA): defined as an infant whose birth weight is less than the 10th percentile for the gestational age. It is based on data derived from an appropriate reference population. The registry will utilize the sex specific international growth reference standards from the International Fetal and Newborn Growth Consortium for the 21st Century (INTERGROWTH-21st) for those born at ≥33 weeks gestational age (Villar, 2014). The INTERGROWTH-21st standards are the latest available global reference standards, representing contemporary information from an international, multiethnic, diverse population and have been specifically developed for modern research. As the INTERGROWTH-21st standards are valid for infants born between 33^{0/7} and 42^{6/7} weeks gestation, SGA will be additionally classified using the reference standard endorsed by the American Congress of Obstetricians and Gynecologists (ACOG) which is applicable for the entire range of gestational age (Alexander, 1996).

4.3.2. Birth Defects

The registry will define and code birth defects with criteria specified by Centers for Disease Control and Prevention (CDC)'s Metropolitan Atlanta Congenital Defects Program (MACDP) (Birth Defects and Genetic Diseases Branch 6 – Digit Code for Reportable Congenital Anomalies, Version 08/07). Newborn and infant conditions that are not necessarily considered birth defects appear in the Exclusion List for the MACDP. These conditions may be included under certain circumstances by CDC criteria and will be considered "conditional defects" in the registry.

The registry will define a defect as any major structural or chromosomal defect or combination of 2 or more of the conditional defects in live-born infants, stillbirths, or fetal losses of any gestational age (including outcomes prior to 20 weeks' gestation or weighing <500 g). This definition is consistent with, but not restricted to, the CDC MACDP definition. Clusters of conditional defects (as defined by CDC MACDP) and data from aborted fetuses of less than 20 weeks' gestation, when available, will be included to increase sensitivity of monitoring. The MACDP includes conditional defects only if in the presence of a major structural defect. In contrast, this registry will consider reports of 2 or more conditional defects as a birth defect case, to increase potential signal generation and to capture instances where a combination of conditional defects might constitute a major birth defect or syndrome.

The registry will conform to the CDC MACDP guidelines in disqualifying birth defects if those findings are present in infants born at less than 36 weeks of gestation and are attributable to prematurity itself, such as patent ductus arteriosus, patent foramen ovale, or inguinal hernias. The CDC MACDP classification includes chromosomal defects. Though these defects are not likely to contribute to a risk for a drug exposure, the registry will include these birth defects to maintain this consistency with the CDC MACDP.

Live-born infants with only transient or infectious conditions or with biochemical abnormalities (e.g., jaundice) will be classified as being without reported birth defects unless there is a possibility that the condition reflects an unrecognized birth defect. Detected and reported transient or infectious conditions or biochemical abnormalities in infants without reported birth defects and defects that are excluded by the CDC guidelines will be reviewed and noted in an appendix in the registry reports.

Because this registry will be conducted in North America and Europe at a minimum, the registry will use the European Surveillance of Congenital Anomalies (EUROCAT) in addition to the US-based CDC MACDP in subgroup-analyses and/or with specific SLE comparator cohorts, if data are available or applicable.

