4.6.8. Registry Case Management and Disposition

4.6.8.1. Prospective Registry Reports

The registry will encourage prospective registration, which is defined as those exposures registered before the end of the pregnancy (i.e., live birth, fetal loss, etc). Two definitions for prospective reports of pregnancy will be used in this registry, traditional prospective and pure prospective [Holmes, 2008; Tomson, 2004]. Traditional prospective reports of pregnancy will include all women who enroll in the registry before the end of pregnancy (live birth, fetal loss, etc), regardless of known normal or abnormal prenatal test results. Pure prospective reports of pregnancy are a subset of traditional prospective reports and include those where (a) the enrollee did not know at the time of enrollment whether the fetus had a malformation, and (b) no prenatal testing was completed prior to enrollment. Reports of pregnancy defined as pure prospective will be included in the primary study population. Section 6 addresses the rationale, potential bias, and analytic techniques that may be employed to attempt to control for any known bias that may be introduced by this practice.

Prospective infant follow-up beyond the first year of life will not be routinely solicited by the registry but follow-up may be extended on a case-by-case basis if deemed medically necessary. In addition, while the study remains active, reports of birth defects that were identified in children after the 1st year of life and by 6 years of age will be entered into the database and reported in registry reports. This age criterion is consistent with CDC MACDP practice (see CDC MACDP Case Definition Criteria, 2015). Prospective reports of birth defects in infants beyond the first year of life and by 6 years of age will not be included in the primary study population, but will be described in the text of the registry final report. Prospective reports of infant infections beyond the first year of life will be forwarded to the sponsor for pharmacovigilance purposes only.

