4.8.2.2. Analysis Parameters for Birth Defects

Most structural defects originate in the first trimester of pregnancy, the period of organogenesis. Therefore, the outcome data for pure prospective evaluable cases will be stratified by the earliest trimester of exposure to belimumab. For this registry, gestational weeks will be estimated from the most reliable EDD as reported by the HCP. If a CEDD is provided by the HCP, it will be used instead. The date of conception will be calculated as the most reliable EDD minus 38 weeks. If the EDD is not available or never estimated, the first day of the LMP may be used to estimate gestational age. The second trimester begins at week 14 after the date of conception or LMP, and the third trimester begins at week 28.

Only cases meeting the CDC MACDP criteria for a defect or with 2 or more conditional defects will be included in the primary study population. Single minor defects do not constitute a birth defect according to the CDC MACDP classification; therefore, they will be listed in the report, but not included in the primary study population.

The birth defect primary analysis will include pure prospective pregnancies and a sensitivity analysis with traditional prospective pregnancies is planned.

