4.8.3.1. Population-Based Birth Defects Surveillance Programs

The Centers for Disease Control and Prevention (CDC) Metropolitan Atlanta Congenital Defects Program (MACDP) classification system will be used as the primary comparator data for defining and coding of birth defects for all registry sites. For the occurrence of birth defects, CDC MACDP data will be used for all sites as it is widely used as a comparator in pregnancy registries. The European Surveillance of Congenital Anomalies (EUROCAT) data will be used as a secondary comparison for European sites.

The primary objectives of CDC MACDP are to regularly and systematically monitor births of malformed infants to monitor changes in incidence or other unusual patterns and to develop a case registry for use in epidemiological studies. CDC MACDP actively searches for birth defects among the 50,000 annual births to residents of metropolitan Atlanta's 5 counties and abstracts medical records at all Atlanta obstetric hospitals, pediatric referral hospitals, genetics laboratories, and vital records [Correa-Villasenor, 2003]. CDC MACDP data have been used as a comparator cohort in examinations of birth defects for other pregnancy registries (acyclovir, sumatriptan, lamotrigine, and zidovudine) [Honein 1999]. The most recent CDC MACDP 5-year prevalence of 2.78% (6,945 cases with birth defects/249,999 live births) from 1999 to 2003 is deemed the most appropriate comparator birth defect data [Correa, 2007], due to lack of adequate birth defect data for the offspring of SLE mothers.

The total prevalence of birth defects overall in EUROCAT (including fetal deaths and pregnancy terminations) from 2004-2008 was 2.33% (http://www.eurocat-network.eu/). EUROCAT is a European network of population-based registries, including 43 registries in 20 countries, and it covers 29% of the European population. It started in 1979 and includes 1.5 million births per year in Europe. Its primary objectives are to provide essential epidemiological information on congenital anomalies and to act as an information and resource center to individuals and public health professionals.

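### The difference from the MACDP 2.78% uses a primary numerator that counts clusters of conditional defects, which by the protocol's own account MACDP does not count

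*Protocol*

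**What the plan says.** Protocol Section 4.3.2 sets the two case rules next to each other. For the comparator: "The MACDP includes conditional defects only if in the presence of a major structural defect". For the registry: "In contrast, this registry will consider reports of 2 or more conditional defects as a birth defect case". The reason given is better signal generation, and the section discloses that the definition goes beyond that of MACDP.

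Section 4.8.2.2 then fixes the rule for the primary analysis: "Only cases meeting the CDC MACDP criteria for a defect or with 2 or more conditional defects will be included".

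Section 4.8.3.1 names the comparator: "CDC MACDP data will be used for all sites as it is widely used as a comparator in pregnancy registries". The figure is also fixed there, at 2.78%, which is 6,945 cases among 249,999 births in the years 1999 to 2003. Section 4.8.4.2 and the Protocol Summary plan the difference between the registry rate and the comparators, with a 95% CI.

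On age at detection, Section 4.6.8.1 says of the by-6-years limit: "This age criterion is consistent with CDC MACDP practice". It then sets a narrower limit for the primary population: "Prospective reports of birth defects in infants beyond the first year of life and by 6 years of age will not be included". Such later reports are described in the text of the final report (Sections 4.6.8.1 and 4.6.8.2).

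**The concern.** A wide case definition suits a registry that looks for signals. The difficulty is that the same wide case set also becomes the numerator of the one quantitative benchmark planned for the primary endpoint. A difference between two prevalences can be read as a possible drug effect only if both count the same thing. Here an infant with two conditional defects and no major defect is a case in the registry but not in MACDP. Even with no drug effect, such infants push the difference upwards.

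The 95% CI describes sampling error around the registry rate as defined. It does not widen or move to reflect a difference in case rule, so a reader of the final report could not separate the two.

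Elsewhere the protocol takes care to align with the comparator. Section 4.3.2 keeps chromosomal defects, though it thinks them unlikely to be drug-related, for consistency with MACDP. Section 4.8.4.2 counts defects in losses at or after 20 weeks so that the rates can be compared. Losses before 20 weeks, another deliberate widening, enter only in an additional analysis. Conditional-only clusters get no such split.

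**Working it through.** **Inputs**
- MACDP prevalence: 6,945/249,999 = 2.78% (Section 4.8.3.1).
- Planned live births: 350, from a range of 311 to 380 (Section 5).
- Stated precision: exact 95% CI 1.32% to 5.09% (Section 5).
- Rate of conditional-only clusters: not given.
- Share of MACDP cases first found after age 1: not given.

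**1. The plan's own figures.** Live births: 500 × 0.95 × 0.80 = 380 and 500 × 0.83 × 0.75 = 311. Expected cases at 350 live births: 350 × 6,945/249,999 = 9.72. The Clopper-Pearson interval with that count is 1.32% to 5.09%. The stated figures reproduce and are not in dispute.

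**2. Effect of one conditional-only case.** It adds 1 to the numerator and nothing to the comparator, so it moves the difference by 1/N:
- N = 311: 1/311 = 0.32 points
- N = 350: 1/350 = 0.29 points
- N = 380: 1/380 = 0.26 points

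At 350 live births one case is 1/9.72, or about 10%, of the expected count.

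**3. Expected difference with no drug effect.** If conditional-only cases occur in a fraction c of live births, and the background rate on the MACDP rule is 2.78%, the expected difference is (2.78% + c) − 2.78% = c. It is zero only if c is zero.

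**4. Illustration, with c assumed.** As a reading device, not a rule in the protocol, take a flag to mean that the exact lower 95% limit exceeds 2.78%. At 350 live births this needs 17 or more cases. The chance of a flag with no drug effect is P(X ≥ 17), with X binomial (350, 2.78% + c):

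| Assumed c (points) | Expected extra cases, 350 × c | Chance of a flag |
|---|---|---|
| 0 | 0 | 2.0% |
| 0.25 | 0.9 | 4.0% |
| 0.5 | 1.75 | 7.2% |
| 1.0 | 3.5 | 17.7% |

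For scale, the half-width of the 95% CI on the difference is 1.96 × √[0.0278 × 0.9722 × (1/350 + 1/249,999)] = 1.7 points. The shift is smaller than the sampling error over this range, but it is systematic.

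**5. Age window, also by assumption.** If detection by age 1 captures a fraction f of what the comparator counts, the expected difference from this feature alone is 2.78 × (f − 1) points: −0.14 at f = 0.95, −0.28 at 0.90, −0.56 at 0.80 and −0.83 at 0.70. No value of f can be taken from the documents, and f = 1 is not excluded. Across these assumed ranges for c and f, the two features together give anything from −0.83 to +1.0 points.

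**The case against.** The wide definition is deliberate, explained and disclosed. Section 7.11 says that the registry exists to find signals, and Sections 4.8.4 and 5 call the comparison descriptive. Section 4.8.3.2 warns that external sources may classify defects differently, and Section 6 adds differences in data source and collection methods. All of that stands, and nothing is concealed. But these cautions concern features of outside data that the registry cannot control. None connects the registry's own choice of case rule to the 2.78% comparison.

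It can also be said that a MACDP-only table belongs in the Reporting and Analysis Plan, which is not shown and may contain one. The point does not rest on that plan's silence, however. The protocol itself fixes the case rule, the comparator and the contrast, and these do not match.

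On age, a reader might infer that the one-year cut-off biases the difference downwards as a matter of fact. The documents do not support so firm a statement. That the 2.78% includes detection up to age 6 is an inference from a remark on MACDP practice. The figure covers 1999 to 2003 and its cited source is dated 2007, so children born in 2002 and 2003 could not have reached age 6 by then.

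A reader might also want a sensitivity analysis that adds defects found between ages 1 and 6. Section 4.6.8.1 does not routinely solicit follow-up after the first year, so this would mix unsolicited reports with the active search that Section 4.8.3.1 ascribes to MACDP. Section 4.6.8.2 already plans to describe these reports.

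**Conclusion.** The mismatch in case rule holds on the protocol's text alone (Sections 4.3.2, 4.8.2.2 and 4.8.4.2). Each conditional-only case inflates the difference from MACDP by 0.29 points at 350 live births. The total cannot be sized, because the documents do not give the expected number of such cases. The chances in the table rest on assumed values of c.

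Three stronger readings go too far:
- That a ratio near 1.3 is to be expected without a drug effect. This needs three conditional-only cases: (9.73 + 3)/350 = 3.64%, and 3.64/2.78 = 1.31. Three in 350 is 0.86% of live births, an assumption that no passage supports.
- That the reported difference is biased upwards overall. The age window may act the other way, to an unknown extent, so the net sign is not determined.
- That the same correction applies to the EUROCAT comparison. The protocol says that the EUROCAT 2.33% includes fetal deaths and terminations, but does not give EUROCAT's rule for conditional defects.

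The age mismatch therefore supports a stated limitation and no more.

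**What to change.** 1. In Sections 4.8.2.2 and 4.8.4.2, base the difference from MACDP on cases that meet MACDP criteria, excluding infants and fetuses whose only findings are conditional defects.
2. Report the count and prevalence with two or more conditional defects included as a separate analysis, labelled as signal detection and tied to Section 7.11. The wide definition in Section 4.3.2 can stay for that purpose.
3. Beside the MACDP difference, state as a limitation that the primary numerator covers the first year of life, whereas the protocol describes a by-6-years criterion as MACDP practice. Add that, taken alone, this could lower the registry rate relative to the comparator to an unknown extent.

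The cost is small. Under Section 7.10 the birth defect evaluator already classifies the reported defects, so one further flag and a few tables are enough. The downside is slightly fewer counted cases in the headline comparison. No case is lost to signal review.

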4.3.3. Serious and/or Clinically Significant Infections in Infants

All infections that meet the serious adverse event criteria as per Section 7.4 will be reported for infants through 12 months of age. Certain non-serious events will additionally be reported as clinically significant and will include:

• Infants from birth through 6 months of age: infections requiring treatment

• Infants from birth through 3 months of age: fevers of unknown origin or of known infectious etiology

4.4. Exposure Definition

For belimumab-exposed subjects: One complete or partial dose of commercially supplied belimumab, administered within the 4 months (i.e., a period of approximately 5 belimumab terminal half-lives) prior to and /or during pregnancy, will constitute exposure. Belimumab exposure will be further categorized by earliest trimester of exposure, as described in Section 4.8.2.2.

For belimumab "unexposed" subjects: Treatment with any immunosuppressants (azathioprine, methotrexate, cyclophosphamide, mycophenolate, biologics or others) as defined in the SABLE protocol as SLE treatment, excluding belimumab (Protocol HGS1006-C1124). There must be sufficient evidence to confirm that exposure to belimumab did not occur within 4 months prior to and / or during pregnancy for a woman to be classified within this group.

4.5. Adverse Drug Experiences / Event Measures

The following outcomes for the registry objectives represent a number of potential adverse drug experiences or events, which include but may not be limited to:

- Reports of congenital anomalies in the fetus or infant
- Reports of adverse pregnancy outcomes, including spontaneous miscarriages and stillbirths
- Reports of serious and/or other clinically significant infections in the infant
- Reports of serious adverse events in the mother or infant

The registry will collect and process all reported serious adverse drug experiences/events as outlined in Section 7.4.

4.6. Data Collection and Management

This is a voluntary registry and the registry awareness program will encourage enrollment as early in pregnancy as possible, so as to minimize bias. In addition, all investigators from the SABLE protocol will be made aware of the Registry and will inform eligible women of their option to co-participate in this Registry. The participants will be followed for the duration of their pregnancies and after birth to ascertain pregnancy and infant outcomes.

The pregnant woman and appropriate members of her health care team will serve as data reporters to the registry. Data regarding participants' SLE disease severity will be sought from the belimumab prescriber to encompass 4 different timepoints (pre-conception, registration, end of second trimester and pregnancy outcome). Data regarding the pregnancy and pregnancy outcome will be sought from the obstetric HCP, and data on live-born infants will be sought from the pediatric HCP. Appropriate members of the woman's and infant's health care team will be contacted to complete missing data as

needed. Participant-reported data will be verified from the HCP overseeing that component of the participant's care. All data will be collected from the participant or the relevant HCP on case report forms (CRF). Medical records will not be requested by the registry unless considered appropriate during targeted follow-up of specific events and outcomes (see Section 4.6.5).

As noted in the following table (Table 1), contact will be made with HCPs at several different time points. Contact with the providers will be timed to maintain interest in the data collection and to minimize loss to follow up. CRF data collection will allow entry of data regardless of when it is obtained and will be associated with gestational age, not with date entered in the CRF. Much of the data collected will be recorded on running logs to facilitate complete data capture.

- Depending on the gestational age at time of enrollment and pregnancy outcome, not all CRFs may be completed for each participant. For example, if a participant enrolls late in pregnancy and delivers early, there may be no second trimester data collection form completed. Additional contacts may occur at the discretion of registry personnel or HCP to complete data collection. At each contact, data from every visit to the HCP since the prior contact between the HCP and the registry will be reviewed for relevance to the registry.
- Belimumab exposures, other SLE treatment, other medications and concurrent medical conditions will be recorded on running logs by the prescriber and obstetric HCPs at each registry contact to capture all relevant data for the pregnancy.
- The data, which are being collected by registry staff, are all clinical data that are routinely documented in medical records during the course of the pregnancy, and may be extracted by the HCPs, thereby minimizing recall bias. All data entered into the registry database will be associated with the gestational age at which the assessment occurred.
- Every clinical event or abnormal value that has been identified will be collected by registry staff regardless of the number of visits the patient makes to any given HCP. All of these data will be associated with the gestational age at which the assessment was made.

To ensure maximum collection of data, the registry will accept data from clinicians at any time from the day a participant is enrolled in the registry through the day that the registry is closed. No date for cessation of data entry into the pregnancy registry on any specific participant will be specified.

The registry will be strictly observational; the schedule of office visits and all treatment regimens will be determined by the treating HCP. There will not be mandatory laboratory tests or assessments required as part of this registry. Only data acquired during the course of routine medical care will be collected, with the possible exception of the PGA of SLE disease activity (Appendix 1) and the SDI (Appendix 2). The PGA is a simple, concise, global index of disease activity that will be completed at registration (including a pre-conception assessment), towards the end of 2nd trimester and at pregnancy outcome for registry participants with SLE. SLE disease activity is often assessed in usual clinical care and collection of this information will be integral to

evaluating disease severity during the pre-conception period through the end of pregnancy. Every effort will be made to collect PGA data for the 6 month period prior to conception, at registration and towards the end of 2nd trimester. In addition, PGA will be collected at pregnancy outcome to reflect disease activity for the entire pregnancy. The SDI records irreversible organ system damage occurring in participants with SLE regardless of etiology. Damage may be attributed to active SLE disease, concomitant medication or intercurrent illness [Gladman, 1996].

Study procedures and enrollment criteria will be consistent among all participants per local laws and regulations.

